## 7.3 Subject Population(s) for Analysis

For both the primary and secondary aims/outcomes, we will study an all-randomized population: Any subject randomized into the study, regardless of whether they received study drug.

We will also collect process data, including barriers and facilitators encountered in the completion of all study procedures. This data will include reason for non-inclusion for all subjects approached but not enrolled.

# 8 Safety and Adverse Events

## 8.1 Definitions

### Unanticipated Problems Involving Risk to Subjects or Others

Any incident, experience, or outcome that meets all of the following criteria:

- Unexpected in nature, severity, or frequency (i.e. not described in study-related documents such as the IRB-approved protocol or consent form, the investigators brochure, etc.)
- Related or possibly related to participation in the research (i.e. possibly related means there is a reasonable possibility that the incident experience, or outcome may have been caused by the procedures involved in the research).
- Suggests that the research places subjects or others at greater risk of harm (including physical, psychological, economic, or social harm).

### Adverse Event

An **adverse event** (AE) is any symptom, sign, illness or experience that develops or worsens in severity during the course of the study. Intercurrent illnesses or injuries should be regarded as adverse events. Abnormal results of diagnostic procedures are considered to be adverse events if the abnormality:

- results in study withdrawal
- is associated with a serious adverse event
- is associated with clinical signs or symptoms
- leads to additional treatment or to further diagnostic tests
- is considered by the investigator to be of clinical significance

### Serious Adverse Event

Adverse events are classified as serious or non-serious. A **serious adverse event** is any AE that is:

- fatal
- life-threatening
- requires or prolongs hospital stay
- results in persistent or significant disability or incapacity
- a congenital anomaly or birth defect
- an important medical event

Important medical events are those that may not be immediately life threatening, but are clearly of major clinical significance. They may jeopardize the subject, and may require intervention to prevent one of the other serious outcomes noted above. For example, drug overdose or abuse, a seizure that did not result in inpatient hospitalization, or intensive treatment of bronchospasm in an emergency department would typically be considered serious.

CONFIDENTIAL

This material is the property of the NYU School of Medicine and Langone Medical Center. Do not disclose or use except as authorized in writing by the study sponsor

All adverse events that do not meet any of the criteria for serious should be regarded as **non-serious adverse events**.

### **Adverse Event Reporting Period**

The study period during which adverse events must be reported is normally defined as the period from the initiation of any study procedures to the end of the study treatment follow-up. For this study, the study treatment follow-up is defined as 30 days following the last administration of study treatment.

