## Study Summary

Title	Novel Interventions for Alcohol Dependent Frequent Emergency Department Users: A phase IV, randomized, open-label, non-placebo-controlled, single-center study of the feasibility, acceptability, and effect of extended-release naltrexone 380mg intramuscular injection compared to standard care on healthcare utilization, drinking, and quality of life in subjects with severe alcohol use disorders and frequent emergency department use.
Short Title	XR-NTX in ED users with AUDs
Protocol Number	S13-00928
Phase	4
Methodology	Randomized, Open Label, non-placebo (compared to standard care)
Study Duration	8 years
Study Center(s)	Single-center
Objectives	To conduct a feasibility and acceptability study of XR-NTX+CM treatment in alcohol dependent patients with frequent ED use and explore its effect on healthcare utilization, drinking, and quality of life.
Number of Subjects	300 (Pilot, N=50; Subsequent trial N=250)
Diagnosis and Main Inclusion Criteria	Alcohol use disorder and frequent emergency department use
Study Product, Dose, Route, Regimen	Extended-release naltrexone (Vivitrol) 380mg intramuscular injection every 4 weeks
Duration of administration	12 months
Reference therapy	Reference is treatment as usual (No medications)
Statistical Methodology	Formal statistical analysis is not planned for the primary aim, in which we will a) further develop and pilot procedures and b) descriptively document feasibility and acceptability of XR-NTX for frequent ED users with alcohol use disorders. To explore the intervention effect, we will generate descriptive statistics and calculate changes in scores within and between groups.

CONFIDENTIAL

This material is the property of the NYU School of Medicine and Langone Medical Center. Do not disclose or use except as authorized in writing by the study sponsor

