2. For subjects randomized to the Standard care arm, the PI/RA will provide referral to Bellevue ambulatory care and/or another suitable substance use treatment program for MM. Facilitating this referral (and offering another referral at the close of the study) is the extent of intervention for this arm. The schedule for research assessment visits is weeks 12, 24, and 48; the time-window during which these research assessments may be conducted will be extremely liberal. If a scheduled date has passed, we will perform a research assessment at the next available opportunity (up to 6 months after the 48 week visit). During research visits, the PI/RA will repeat the assessments that were conducted at the initial enrollment visit plus adverse events and subject satisfaction and we will collect a 17mL blood sample to examine alcohol consumption biomarkers. Subject participation ends after the week-48 research visit.

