### Both Arms, Clinical Visit - Medical Management (MM) Visit (Ambulatory Care or ED)

- Subjects in both arms will be referred to Bellevue ambulatory care as scheduled for an initial visit for Alcohol-Medical Management (MM) to assess and manage adverse events, treatment effects, and support the goals of reducing the harms associated with alcohol use.
- Data will be extracted from the clinical note, including adverse events or concerns.
- Subjects in intervention arm who miss appointment will be contacted through methods described in Section 4.4.2. Follow up will be performed in the ED if subject cannot be navigated to ambulatory care. Subjects will be given a week 4 appointment.
- Subjects in the Standard Care Arm have no further clinical intervention beyond the initial referral but will have research assessments at weeks 12, 24, and 48. Any ongoing medical care will be left to the discretion of their (non-study) treating providers.

CONFIDENTIAL

This material is the property of the NYU School of Medicine and Langone Medical Center. Do not disclose or use except as authorized in writing by the study sponsor

### 6.3 Visit 3: Week 4

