## 8.2 Recording of Adverse Events

At each contact with the subject, the investigator must seek information on adverse events by specific questioning and, as appropriate, by examination. Information on all adverse events should be recorded immediately in the source document, and also in the appropriate adverse event module of the case report form (CRF). All clearly related signs, symptoms, and abnormal diagnostic procedures results should be recorded in the source document, though should be grouped under one diagnosis.

All adverse events occurring during the study period will be recorded. The clinical course of each event should be followed until resolution, stabilization, or until it has been determined that the study treatment or participation is not the cause. Serious adverse events that are still ongoing at the end of the study period must be followed up to determine the final outcome. Any serious adverse event that occurs after the study period and is considered to be possibly related to the study treatment or study participation should be recorded and reported immediately.

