#### Report of Changes or Amendments to the Protocol

All proposed changes/amendments to the protocol will be filed with the IRB. IRB approval of such amendments will be forwarded to the NIAAA project officer, and the original amendment approvals will be filed in the primary document manual.

In the present protocol, there are no plans for interim analysis of safety or effectiveness data (see above). However, the PI and Key Personnel will examine safety data on an ongoing basis. Adverse experience

CONFIDENTIAL

This material is the property of the NYU School of Medicine and Langone Medical Center. Do not disclose or use except as authorized in writing by the study sponsor

and safety contrasts will be performed as indicated, in response to recommendations by the PI. If interim analysis of safety data is deemed advisable by NIAAA or our IRB, we will enact such a plan.

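### The adverse event reporting period is tied to the last injection, so it has no end in standard care and depends on adherence in the intervention arm; with unequal questioning, raw adverse event counts are not comparable between arms

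*Combined protocol and SAP*

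**What the plan says.** Section 8.1 (Adverse Event Reporting Period) describes the period as "normally defined as the period from the initiation of any study procedures to the end of the study treatment follow-up" and then fixes its end: "For this study, the study treatment follow-up is defined as 30 days following the last administration of study treatment". It gives no rule for subjects who receive no study treatment. Standard care is such an arm. The Study Summary lists its reference therapy as usual treatment without medication, and Section 3.1 says of the referral: "Facilitating this referral (and offering another referral at the close of the study) is the extent of intervention for this arm".

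Section 8.2 governs how events are found: "At each contact with the subject, the investigator must seek information on adverse events by specific questioning". Sections 6.3 to 6.13 place an adverse event assessment at each injection visit, in the intervention arm only. Sections 6.5, 6.8 and 6.14 place one at the week 12, 24 and 48 research visits in both arms. At week 1 both arms are referred to a clinic visit (Section 6.2), where "Data will be extracted from the clinical note, including adverse events or concerns". After that, "Subjects in the Standard Care Arm have no further clinical intervention beyond the initial referral", apart from the three research assessments.

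Other text is wider than the dose-based rule. The definition of an adverse event in Section 8.1 covers anything that arises or worsens while the study runs. The paragraph on physical examination findings requires new abnormalities at the end of the study to be recorded. Section 8.6.1 requires all adverse events in follow-up to be reported.

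On use of the data, Section 8.6.1 says "safety contrasts will be performed as indicated, in response to recommendations by the PI". Sections 8.5 and 8.6.1 note that the DSMB can compare the two groups at each review because the trial is open-label.

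**The concern.** A reporting period must have a start and an end in both arms before a count, or a rate per person-time, means anything. Here one arm has no end date, and in the other the end is set by how long the subject stays on the drug. Missed and resumed injections are expected (Table 2, Section 4.4.1, Section 6), so short periods may be common. The subjects with the shortest periods are those who stopped early.

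The arm with the drop-out-dependent period is also the arm asked about events more often. The two faults push in opposite directions: truncation lowers the intervention count and extra contacts raise it. Someone reading a raw table of events by arm could not tell the sign of the net bias. The DSMB would be that reader, in an open-label trial with no blinding to even out how staff apply an ambiguous rule.

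**Working it through.** **Inputs.** Injections at day 0 and weeks 4, 8, 12, 16, 20 and 24, with potential additional injections at weeks 28, 32, 36, 40 and 44, up to 12 in total (Section 3.1). Planned medication is 6 months, with continuation up to 12 months to be explored (Section 5.2). Research visits in both arms at weeks 12, 24 and 48. Week-1 clinic visit in both arms (Section 6.2).

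**The plan's own figure.** 1 + 6 + 5 = 12 injections, which matches Section 3.1.

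**End of the reporting period.** Day = 7 × week of last injection + 30.

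| Last injection | Period ends | Share of 336 days |
|---|---|---|
| Day 0 only | day 30 | 30/336 = 8.9% |
| Week 20 | 140 + 30 = day 170 | 50.6% |
| Week 24 | 168 + 30 = day 198 | 58.9% |
| Week 44 | 308 + 30 = day 338 | all |
| Week 52 | 364 + 30 = day 394 | all |
| Standard care | not defined | not defined |

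The week-48 assessment is at 7 × 48 = day 336. It lies 336 − 198 = 138 days past the end for a subject whose last injection is at week 24. For a subject with one injection, all three research visits (days 84, 168 and 336) lie past the end.

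Weeks 20 and 24 both appear because Section 3.1 puts the week-24 injection on the main schedule while Table 2 marks it as extension. Week 52 appears because the closing of the injection window is given as the 48th week (Table 2), the 12th month (Section 4.4.1) and 52 weeks (Section 6). These passages must be reconciled, since each moves the end of the period.

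**Scheduled adverse event visits after enrolment**, counted as distinct weeks and assuming full attendance:

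- Standard care: weeks 1, 12, 24, 48 = 4.
- Intervention, planned course: weeks 1, 4, 8, 12, 16, 20, 24, 48 = 8; 8/4 = 2.0.
- Intervention, full optional extension: add weeks 28, 32, 36, 40, 44 = 13; 13/4 = 3.25.

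**What that could do to event counts.** The documents give no recall period, so this part is an assumption shown as a range. Suppose each visit picks up events from the preceding L days only, over days 1 to 336, and set the dose-based cut-off aside.

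| Recall L | Days covered: standard / 6-month / 12-month | Ratio to standard: 6-month, 12-month |
|---|---|---|
| 28 days | 91 / 196 / 336 | 2.15, 3.69 |
| 60 days | 187 / 228 / 336 | 1.22, 1.80 |
| 90 days | 258 / 258 / 336 | 1.00, 1.30 |
| 168 days or more | 336 / 336 / 336 | 1.00, 1.00 |

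For example, at 28 days standard care covers 7 + 3 × 28 = 91 days. The 6-month course covers 168 + 28 = 196, and 196/91 = 2.15.

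**After the fix.** With one calendar period and only the week 12, 24 and 48 visits, the count is 3 against 3.

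**The case against.** The strongest reply is that Section 8.1 should not be read alone. The wider wording elsewhere would keep events after early discontinuation. Non-adherent subjects are not withdrawn (Section 4.4.1) and keep their research visits, and Section 8.2 still requires later serious events that are possibly related to be reported. A reader might infer from the 30-day rule that events after stopping are simply lost. The documents do not support that, and the 8.9% figure follows only from the reporting-period paragraph taken by itself. What this establishes, though, is a contradiction rather than a cure. Section 8.2 records events in the study period, which is the very term that the reporting-period paragraph defines, and nothing says which text prevails.

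A reader might also infer that safety cannot be compared at all. That goes too far. Both arms have adverse event collection at weeks 1, 12, 24 and 48, liver enzymes at enrolment and months 3, 6 and 12 (Section 1.6.1), and mortality from vital statistics (Sections 3.4 and 4.4.2). Hospital and ED use comes from databases, where available (Section 7.2.2).

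A third inference is three times the visits and hence a 3:1 ratio of events. The visit figure needs the full optional extension, and both visit ratios assume an attendance that the plan does not expect. The event ratio needs a short recall period that the documents never state.

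Finally, no formal between-arm safety analysis is specified, and the sentence on safety contrasts does not say that they are between arms; the same section plans no interim analysis of safety. This is fair and limits the weight of the point. The DSMB's ability to compare the groups is the firmer ground. The Data and Safety Monitoring Plan (Attachment 8) is listed but is not among the text available here, and it may say more.

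**Conclusion.** The point holds in a limited form. The end of the reporting period is undefined for standard care and adherence-dependent for the intervention arm. It excludes the week-48 assessment for subjects completing the planned 6-month course, and it conflicts with other text in Sections 8.1 and 8.6.1. All this follows from the wording and needs no assumption beyond the visit schedule.

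Scheduled ascertainment is 2.0 to 3.25 times as frequent in the intervention arm with full attendance. Raw counts or rates of all recorded adverse events are therefore not comparable between arms. The size of that bias cannot be fixed from the documents. Under assumed recall of 28 days the ratio of covered days is 2.15 to 3.69, and it falls to 1.00 at 168 days or more. Mortality, scheduled liver enzymes and events from shared visits remain comparable. No formal safety test is affected. What is at risk is the reading of event tables by the DSMB and in any contrast made later.

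**What to change.** Set one calendar reporting period for both arms: enrolment to a fixed day (for example day 336), or 30 days after the last injection if that is later. Cut every between-arm summary at the fixed day. A fixed day is better than the date of the week-48 visit, because overdue assessments may be held up to 6 months after week 48 (Section 3.1). Reword the reporting-period paragraph, the definition and end-of-study paragraphs of Section 8.1, and Sections 8.2 and 8.6.1, so that all use this period.

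Base any between-arm adverse event summary, including what the DSMB sees, on the shared research visits at weeks 12, 24 and 48 plus mortality and available hospital records, expressed per person-time. State the look-back for the adverse event questions at those visits, the same in both arms. List events found only at injection visits separately. Leave week 1 out of the shared set, because Section 6.2 states pursuit of missed week-1 visits for the intervention arm only.

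Reconcile the status of the week-24 injection (Section 3.1 against Table 2) and the three statements of when the injection window closes.

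The cost is protocol wording, one extra table, and slightly more reporting for subjects who stop injections early. Making the change early matters because events that are never collected cannot be fully recovered.

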### **Preexisting Condition**

A preexisting condition is one that is present at the start of the study. A preexisting condition should be recorded as an adverse event if the frequency, intensity, or the character of the condition worsens during the study period. By definition, all subjects in this study population have the pre-existing condition of frequent use of acute medical services, including ambulance transports, emergency department visits, and inpatient and outpatient admissions for detoxification and other alcohol-related problems, injuries, and consequences.)

### **General Physical Examination Findings**

At screening, any clinically significant abnormality should be recorded as a preexisting condition. At the end of the study, any new clinically significant findings/abnormalities that meet the definition of an adverse event must also be recorded and documented as an adverse event.

### **Post-study Adverse Event**

All unresolved adverse events should be followed by the investigator until the events are resolved, the subject is lost to follow-up, or the adverse event is otherwise explained. At the last scheduled visit, the investigator should instruct each subject to report any subsequent event(s) that the subject, or the subject's personal physician, believes might reasonably be related to participation in this study. The investigator should notify the study sponsor of any death or adverse event occurring at any time after a subject has discontinued or terminated study participation that may reasonably be related to this study. The sponsor should also be notified if the investigator should become aware of the development of cancer or of a congenital anomaly in a subsequently conceived offspring of a subject that has participated in this study.

### **Abnormal Laboratory Values**

A clinical laboratory abnormality should be documented as an adverse event if any one of the following conditions is met:

- The laboratory abnormality is not otherwise refuted by a repeat test to confirm the abnormality
- The abnormality suggests a disease and/or organ toxicity
- The abnormality is of a degree that requires active management; e.g. change of dose, discontinuation of the drug, more frequent follow-up assessments, further diagnostic investigation, etc.

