Protection against Risk (XR-NTX): As per exclusion criteria, the PI will avoid administering XR-NTX in patients with medical conditions that would contraindicate its use. Specifically, XR-NTX will not be used in: active opioid dependence (including any individual whose urine drug screen is positive for opioids), acute or chronic pain requiring opioid treatment, acute liver injury/failure (liver aminotransferase concentrations  $>5$  times the upper limit of normal), any medical condition considered by the PI to be incompatible with or unsafe for study inclusion (e.g. expectation of future opioid needs), lack of decisional capacity, refusal to consent, currently being prescribed outpatient addiction pharmacotherapy (other than treatment of alcohol withdrawal), previous significant adverse reaction to naltrexone, poly(lactide-co-glycolide, carboxymethylcellulose, or any other components of the diluent, body habitus that precludes safe injection, children, or pregnancy. The PI will assess liver function prior to enrollment; persons with liver aminotransferase concentrations  $>5$  times the upper limit of normal will not be eligible for enrollment. Subjects will be monitored for signs and symptoms of liver injury at subsequent XR-NTX administration visits and research visits. Subjects in both arms will have their liver enzymes tested at enrollment and at the 3-, 6-, and 12-month research visits. The PI will repeat liver enzyme testing if subject receiving XR-NTX through the study has signs or symptoms of liver injury. If the liver aminotransferase concentrations rise to  $>5$  times the upper limit of normal, the laboratory tests will be repeated in one week. If liver enzymes are persistently elevated or if the individual is symptomatic, study medication will be discontinued and the subject will be referred for a Hepatology evaluation.

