Research Assessments (Aim 2): We will collect demographic information and assess a broad range of subject characteristics using validated, reliable questionnaires and other instruments that are widely-used, including in ongoing XR-NTX studies, and for which trainings are available. Data collection at enrollment and months 3, 6, and 12 will include several outcome variables of interest that we have broadly classified as drinking metrics, healthcare utilization, and quality of life. The 30-day Timeline Follow-Back (TLFB) for heavy drinking days is the standard method for assessing self-reported alcohol consumption. The Economic Form 90 notably was used in the COMBINE study and is currently in use by in ongoing alcohol research for assessment of a broad range of health and public sector services utilization (including medical, self-help, legal services) and cost-effectiveness analyses. The Short Index of Problems Related to Alcohol (SIP-2R), and EuroQol-5D (EQ-5D) will be used for quality of life assessments. We will also conduct a 30-minute semi-structured qualitative interview and assess craving (Penn Alcohol Craving Scale), Self-Efficacy (Alcohol Abstinence Self-Efficacy Scale (AASE)), and Patient Motivation and Satisfaction scales. We will collect blood levels of carbohydrate deficient transferrin and GGT, which are biomarkers used together to objectively quantitate heavy drinking. We will ascertain healthcare utilization by triangulating data from Bellevue/HHC hospitals databases, EMS ambulance transports to all NYC EDs, Medicaid claims data, and subject self-report.

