At these meetings, [name] and other research personnel will report on the trial status, followed by a closed session under the direction of the DSMB chairperson, during which time the investigators and research team may be present. This will be followed by an executive session restricted to DSMB members. Issues discussed may include those related to subject safety and benefit, whether the primary study question is being answered, conflict of interest, confidentiality, and ongoing study review (including AEs, SAEs, and regulatory issues).

All adverse events and unanticipated problems during follow-up will be reported to the IRB, DSMB, and NIAAA. Serious adverse events and unanticipated problems will be reported to the IRB and to the NIAAA project officer within 48 hours of it becoming known to the investigator, using the appropriate forms found on the website. The PI and DSMB will conduct a review of all adverse events upon completion of study subjects. The PI will evaluate the frequency and severity of the adverse events and determine if modifications to the protocol or consent form are required.

During the review process, the DSMB will evaluate whether the study should continue unchanged, require modification/amendment, continue or close to enrollment. Either the principal investigator, DSMB, or the NYU IRB have the authority to stop or suspend the study or require modifications. Following each DSMB meeting, recommendations will be made by the chairperson to [name] and a final report (edited by all DSMB members) will be prepared and submitted to NIAAA, the NYUMC IRB, and (if required) the FDA.

Stopping the trial due to safety concerns or interim analysis of the primary outcome are not anticipated; the study medication, XR-NTX, is FDA-approved, its use in this trial is consistent with its FDA labeling, and no significant safety issues have arisen in national post-marketing use. DSM Plans typically include stopping rules that specify the outcome differences detected between groups during an interim analysis that can result in stopping the clinical trial. In general, stopping rules will reflect one of the following conditions: 1) there is clear evidence of harm or harmful side-effects of the treatment; 2) there is not

CONFIDENTIAL

This material is the property of the NYU School of Medicine and Langone Medical Center. Do not disclose or use except as authorized in writing by the study sponsor

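### Section 8.1 gives two unreconciled rules for laboratory adverse events, and the looser one has no size, baseline or clinical-significance threshold

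*Combined protocol and SAP*

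**What the plan says.** Section 8.1, Adverse Event, defines an AE as "any symptom, sign, illness or experience that develops or worsens in severity during the course of the study". It then says: "Abnormal results of diagnostic procedures are considered to be adverse events if the abnormality" meets one of five conditions. These are that it results in withdrawal, accompanies a serious AE, accompanies signs or symptoms, prompts treatment or further tests, or "is considered by the investigator to be of clinical significance".

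Section 8.1, Abnormal Laboratory Values, gives a second list: "A clinical laboratory abnormality should be documented as an adverse event if any one of the following conditions is met". The first of its three conditions is "The laboratory abnormality is not otherwise refuted by a repeat test to confirm the abnormality". The other two are a suggestion of disease or organ toxicity, and a need for active management. The section neither refers to the general definition nor says which list governs.

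Section 8.1, Preexisting Condition, records a condition present at the start as an AE only when it worsens.

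GGT has two roles. Section 3.4 lists it with AST and ALT among the safety laboratory tests. Section 7.2.1 describes CDT and GGT as "biomarkers used together to objectively quantitate heavy drinking", and Section 7.2.2 (Aim 2) assesses them as measures of change in drinking.

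The AE record is used. Section 8.6.1 states: "All adverse events and unanticipated problems during follow-up will be reported to the IRB, DSMB, and NIAAA". The principal investigator also evaluates AE frequency and severity to decide whether the protocol or consent form needs changing.

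**The concern.** Because any one condition is enough, the repeat-test condition stands alone. A result that nobody repeats has not been refuted, so the condition is met by default. It absorbs nearly everything that the other two laboratory conditions would select.

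This population makes that matter. Inclusion requires regular heavy drinking, Section 4.2 admits subjects with aminotransferases up to 5 times the upper limit of normal, and there is no entry limit on GGT. Out-of-range liver enzymes during follow-up are to be expected.

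Two staff members could classify the same result differently, and each could point to a rule in Section 8.1. At stake is the AE profile seen by the oversight bodies, for a drug whose boxed liver warning is noted in Section 1.6.1. There is also a workload cost, because Section 8.2 requires each AE to be followed until it resolves, stabilises or is found not to be caused by the study.

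**Working it through.** The plan states no expected laboratory AE rate, so there is no figure to reproduce. The check sets the rules side by side, then counts the testing occasions.

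**Step 1. Classify typical results under each rule.**

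| Result | Laboratory list, read alone | General definition and preexisting-condition rule |
|---|---|---|
| New or worse, with signs or symptoms | AE | AE |
| New or worse, judged clinically significant | AE unless refuted on repeat and neither other condition applies | AE |
| New or worse, no symptoms, no action, judged not significant, never repeated | AE | None of the five conditions met |
| Raised at enrolment, unchanged or improved | First condition met if never refuted | Not an AE, because nothing has developed or worsened |

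The third row is the clear gap. The fourth is resolved if the parts of Section 8.1 are read together, but the laboratory list does not say that they should be. A value that is repeated is less clear-cut, since the general list counts results that lead to further tests.

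**Step 2. How often is a repeat planned?** Section 1.6.1 gives two triggers. If aminotransferases exceed 5 times the upper limit, "the laboratory tests will be repeated in one week". Liver enzymes are also retested if a subject receiving XR-NTX has signs or symptoms of liver injury. An asymptomatic rise below that aminotransferase level, or an asymptomatic rise in GGT alone, triggers no repeat before the next scheduled panel.

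**Step 3. Count the panels.**
- Routine post-enrolment panels in both arms: weeks 12, 24 and 48 (Sections 6.5, 6.8 and 6.14), so 3.
- Injection visits at weeks 4 to 44: 11, of which 2 (weeks 12 and 24) coincide with research visits. That leaves 11 − 2 = 9 further occasions in the intervention arm, or 3 + 9 = 12 in all.
- Liver enzymes at injection visits are drawn only for signs or symptoms of liver injury (Section 6.3 onward). Abnormal findings on those draws will generally satisfy the general definition already.

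The repeat-test condition therefore mainly adds asymptomatic findings from the 3 panels common to both arms.

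**Step 4. Illustration only.** Let p be the chance that one test shows a new or worsened out-of-range value. The documents give no p, so the values below are assumed. With n independent results, P(at least one) = 1 − (1 − p)^n.

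| Assumed p | GGT only, n = 3 | AST, ALT and GGT, n = 3 × 3 = 9 |
|---|---|---|
| 2.5% | 7.3% | 20.4% |
| 5% | 14.3% | 37.0% |
| 10% | 27.1% | 61.3% |
| 20% | 48.8% | 86.6% |

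For example, 1 − 0.90^3 = 0.271 and 1 − 0.90^9 = 0.613. For a given p these lean high. Enzyme results within a subject are likely to be positively correlated, visits will be missed, Section 8.2 groups clearly related findings under one diagnosis, and the AE reporting period ends 30 days after the last study treatment. The spread shows that the effect could be small or material, depending on a rate that the plan does not supply.

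**The case against.** The strongest reply is that the lists do not conflict. The general definition says that a result is an AE if a condition holds, not only if, so the laboratory list can be read as a broader supplement. That stands: the rules are unreconciled, not logically opposed. A broader list with no stated precedence still leaves the third row of the table open to either coding.

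A reader might infer that a GGT falling during treatment, though still above normal, counts both as an improvement and as an AE. Section 8.1 as a whole does not support this. The general definition requires something new or worse, and the preexisting-condition rule requires worsening.

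A reader might also infer a spurious hepatic excess on XR-NTX from the extra injection-visit panels. The documents do not support that either. Those draws are prompted by signs or symptoms, so removing the repeat-test condition would not remove the findings, and the routine panels are the same in both arms.

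Finally, a reader might conclude that hepatic safety becomes uninterpretable. It does not. AST and ALT can be tabulated apart from GGT, Section 1.6.1 has its own aminotransferase rule, and no hepatic AE endpoint or formal between-arm AE test is planned. It is also true that a later scheduled panel could serve as a repeat, but the plan does not say whether it does.

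**Conclusion.** The point holds as an inconsistency in AE recording. A new or worsened enzyme value that is asymptomatic, needs no action, is judged not clinically significant and is never repeated is an AE under the laboratory list and meets no condition in the general one. The likely result is inflated and inconsistently recorded laboratory AE counts in both arms, with GGT most exposed because it is also a drinking measure.

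The size cannot be derived from the documents. The percentages above rest on assumed rates and independence, and show only a range. It would also be wrong to multiply an assumed prevalence of abnormal panels by the three visits: prevalence includes values that have not worsened since enrolment, and a persistent abnormality would be counted again at each visit although Section 8.2 follows it as one event. No bias between arms from the repeat-test condition is shown.

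**What to change.** In Section 8.1, Abnormal Laboratory Values:

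1. Delete the repeat-test condition as a criterion sufficient on its own, and refer to the five conditions under Adverse Event.
2. State that the new-or-worse requirement and the preexisting-condition rule apply to laboratory values, judged against the subject's enrolment value.
3. State that a change in GGT or CDT is analysed as an outcome, and recorded as an AE only if it meets those conditions.

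The replacement should point to the existing general list. A new, stricter laboratory rule requiring several conditions at once could leave out results that the general list captures, such as those accompanying a serious AE or symptoms, and would create a fresh inconsistency.

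The cost is a few lines of protocol wording. The downside is that minor abnormalities judged not clinically significant would no longer be logged as AEs. Their values remain in the database and can be tabulated by arm and visit.
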